7.3 Adverse Events and Serious Adverse Events	25
7.4 Reporting Procedures.....	26
Adverse Event Reporting.....	26
7.5 Follow-up for Adverse Events.....	26
7.6 Safety Monitoring	27
8. INTERVENTION DISCONTINUATION	27
9. STATISTICAL CONSIDERATIONS	28
9.1 General Design Issues.....	28
9.2 Sample Size and Randomization	28
Treatment Assignment Procedures	29
9.3 Definition of Populations.....	29
Intent to treat (ITT): Intent to treat is defined as the population that has been randomized, regardless of class attendance.	29
9.4 Interim Analyses and Stopping Rules.....	29
9.5 Outcomes	30
9.5.1 Primary Outcome.....	30
9.5.2 Secondary Outcomes	30
9.6 Data Analyses	30
10. DATA COLLECTION AND QUALITY ASSURANCE	31
10.1 Data Collection Forms	31
10.2 Data Management	31
10.3 Quality Assurance.....	32
10.3.1 Training.....	32
10.3.3 Metrics	32
10.3.4 Protocol Deviations	32
10.3.5 Monitoring	32
11. PARTICIPANT RIGHTS AND CONFIDENTIALITY	33
11.1 Institutional Review Board (IRB) Review	33
11.2 Informed Consent Forms	33
11.3 Participant Confidentiality	33
11.4 Study Discontinuation	33

13. PUBLICATION OF RESEARCH FINDINGS.....	33
14. REFERENCES	33
15. SUPPLEMENTS/APPENDICES	37
i. Consent form	37

STUDY TEAM ROSTER

[name]	[contact]	[contact]
[name]	[contact]	[contact]
[name]	[contact]	[contact]
[name]	[contact]	[contact]
[name]	[contact]	[contact]
[name]	[contact]	[contact]
[name], BA	[contact]	[contact]
[name], BA	[contact]	[contact]
[name], BA	[contact]	[contact]

PRÉCIS

Study Title

Delish Study: Diabetes Education to Lower Insulin, Sugars, and Hunger

(AKA Optimizing lifestyle interventions with mindfulness-based strategies in type 2 diabetes)

Objectives

R61 Specific Aims: We will enroll 60 persons with T2DM who will attend an in-person group course providing education on a carbohydrate-restricted (CR) diet. We plan 3 waves of about 20 persons each with 12 weekly sessions. We will randomize participants to receive basic behavioral strategies and diet education alone (Ed) or this same material with added MBI components (Ed+MBI), using a 1:1 ratio (Ed: Ed+MBI). We will use ecological momentary assessment (EMA) methods (via smartphone) to capture changes in eating in response to food cravings or difficult emotions. We will assess dietary adherence using ketone measures and 24-hour dietary recall. We will address the following specific aims:

1. Determine if our EMA measures of behavioral mechanisms have high response rates (> 90%) and are ready for R33 use.
2. Determine if there is preliminary evidence that the MBI intervention impacts our hypothesized mechanisms of action and that the proposed mechanisms predict improved dietary adherence.
3. Assess feasibility and acceptability of two intensities of maintenance (monthly group meetings alone or supplemented by individualized attention) to ensure they are ready for R33 testing.

R33 Specific Aims: We will randomize 120 persons with diabetes in a 1:2 ratio to the Ed (n=40) vs. Ed+MBI (n=80) arms and follow them for 12 months. After the 12-week intervention, we will observe participant for 8 weeks and then re-randomize them using an adaptive intervention design to receive further observation, light maintenance training, or intensive maintenance training, depending on level of adherence achieved during the observation period. We will address the following specific aims:

1. Test whether our proposed behavioral mechanisms (decreased eating in response to cravings or difficult emotions) predict dietary adherence.
2. Test the hypothesis that the Ed+MBI arm will have better dietary adherence than the Ed arm.
3. Compare randomized arms in the adaptive maintenance intervention design to optimize maintenance phase dosing in future trials.
4. Obtain preliminary assessment of intervention effects on clinical outcomes

Design and Outcomes

This is a two-phase study. Both phases will use a randomized, controlled trial design. After pilot testing in the first phase, the second phase will include employing an adaptive intervention design in the post-treatment phase to test optimization of the maintenance intervention (i.e. assigning maintenance intensity/dose based on how a participant is doing).

Interventions and Duration

Participants will attend 12-weekly study intervention classes based on their random assignment: either Education alone (Ed) or Education+Mindfulness (Ed+MBI). Both groups will learn and follow a CR diet, and will participate in maintenance phase activities. If assigned to Ed+MBI, they will also learn and practice mindfulness-based skills.

Sample Size and Population

Target sample size: 180 total (60 participants in the first/R61 phase, 120 in the second/R33 phase).

1. STUDY OBJECTIVES

Our overall hypothesis is that improved ability to manage food cravings and emotional eating is a key mechanism through which mindfulness-enhancements can improve dietary adherence.

In the initial R61 phase, we will look for preliminary evidence for several hypothesized pathways by which the MBI components will influence dietary adherence. These pathways and their associated measures are as follows:

1.1 Primary Objective

Primary mechanistic outcome(s): This study is aimed at testing behavioral mechanisms by which training in mindful eating may improve dietary adherence. Our primary hypothesized mechanism is reduction in **frequency of eating in response to cravings** as a result of enhanced ability to address food cravings with mindfulness training. Our key measure of this mechanism is frequency of eating in response to cravings using ecological momentary assessment (EMA).

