Mindfulness skills have the potential to enhance dietary adherence. We address an area NCCIH identifies as a high priority for mind-body intervention research in RFA-AT-16-005: “behavior change to promote healthy behaviors such as healthy eating.” Jon Kabat-Zinn developed the Mindfulness-Based Stress Reduction (MBSR) program and describes mindfulness as “paying attention on purpose, in the present moment, and nonjudgmentally, to the unfolding of experience moment to moment.” One hypothesized mechanism by which mindfulness may increase long-term dietary adherence is by equipping individuals with the skills to acknowledge and experience food cravings and negative emotions without acting on them and by increasing resilience after temporary lapses in dietary adherence. Mindfulness approaches seek to strengthen abilities to become aware of, tolerate, and adaptively self-regulate uncomfortable sensations (e.g., food cravings) without maladaptive responding (e.g., craving-related eating).¹⁴ Current neurobehavioral models of eating behavior are based on experimental data showing that obese persons respond to pictures of high-calorie foods with greater activation of brain regions hypothesized to mediate motivational effects of food cues.¹⁵ This suggests that heightened sensitivity to palatable food cues may confer greater vulnerability to overeating. Other experimental data show that greater sensitivity to palatable food cues is associated with increased palatable food intake only in persons with lower inhibitory control.¹⁶ These data suggest that strengthening inhibitory control may enhance dietary adherence, and may be especially useful for individuals who are more susceptible to palatable food cues. Mindful awareness of one’s own experience, a core focus of mindfulness training, can reduce both impulsive responses to attractive food stimuli and the thoughts that they trigger in experimental situations.¹⁷

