Intervention content for the Mindfulness program: In addition to the diet components, participants randomized to the Ed+MBI group will receive MBI components using the Eat Right Now (ERN) platform. This will consist of two integrated components: 1) use of the ERN app at home, during the week, to learn and practice mindfulness skills for food-cravings and eating, and 2) in-person group-based discussions of how the mindful eating practices are going, trouble-shooting obstacles/pain points, and doing group exercises and reflecting on them. The Eat Right Now program provides brief videos of 2 to 6 minutes in length on mindfulness and mindful eating topics. Participants can watch the video segments for the week at the beginning of in-person sessions each week. The video segments can also be viewed on a smartphone or tablet at home in a self-paced manner. In person sessions will be led by an experienced mindfulness instructor with training in mindful eating and familiarity with a CR diet for T2DM, and will focus on discussion of how the mindful eating practices are going, trouble-shooting obstacles/pain points, and doing group exercises and reflecting on them. The Eat Right Now app also includes the audio tracks of meditation exercises are core components of our mindful eating program (e.g. body scan, mindful eating practices) that participants can access at any time – which will allow them to cultivate their mindfulness practice in the context of their daily lives. Twelve one-hour sessions addressing mindful eating will be conducted weekly for 12-weeks (monthly during maintenance), before each diet session. The key content of the mindful eating intervention components focuses on: helping people improve their relationship with food and control food cravings, using mindful eating approaches including: paying attention, noticing habit loops, understanding brain science and food/sugar addiction, disrupting emotional and stress eating, cultivating acceptance and curiosity, learning lovingkindness, detaching from thoughts, using healthy restraint, and maintaining motivation.

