improve diet adherence is through reducing eating behavior in response to food cravings. This mobile, real-time EMA approach allows us to capture eating-related behavior and that is often brief and automatic and therefore poorly suited to traditional retrospective questionnaires. Participants will complete EMA of food cravings and craving-related eating via smartphones prior to, during, and following the intervention, a total of up to 6 times. During each of these craving-assessment periods, participants will receive mobile cravings assessment via text 3 times per day for 3 days. The text message will ask them to complete a short questionnaire regarding whether they have experienced any food-related cravings in the past few hours, whether they have eaten in response to these cravings, and what they ate. They will also be asked to rate their stress level during the day.

Computerized Cognitive Measures: The computer session will comprise approximately 20-30 minutes of the tasks described below. These tasks can be adjusted to be shorter than their stated length by reducing the number of trials administered. This is a common practice in neuropsychological science research. We will create a 20-30 minute battery from the following tasks:

- Delayed Discounting³⁷; The DD (1 minute) assesses the extent to which individuals value delayed versus proximal rewards. Individuals who discount delayed rewards at a high rate are more likely to engage in substance abuse, overeating, or problem gambling. This 5-trial adaptation of the original Delayed Discounting,³⁸ task has been validated and is an effective way to assess discount rates while reducing participant burden. The primary outcome is the participant's point of indifference, which is computed with intertemporal choice tasks that present a series of discrete choices between a larger quantity of a reward that is delayed and a smaller amount of that commodity that is available immediately.

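### The primary EMA outcome counts eating only when the participant attributes it to a craving, and only Ed+MBI trains craving awareness, so a change in labelling cannot be told apart from a change in eating

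*Combined protocol and SAP*

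**What the plan says.** Sections 1.1, 3 and 9.5.1 make the EMA frequency of craving-driven eating the primary mechanistic outcome: "Our key measure of this mechanism is frequency of eating in response to cravings using ecological momentary assessment (EMA".

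Section 6.2.2 (Craving EMA) describes the survey. In each period, "participants will receive mobile cravings assessment via text 3 times per day for 3 days". The questionnaire asks about "any food-related cravings in the past few hours, whether they have eaten in response to these cravings, and what they ate", and about stress during the day. No item on eating regardless of craving is described. The second EMA measure in section 9.1, on high-carbohydrate or sweet foods, is also tied to cravings.

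Section 2.2 gives the aim of the training: "Mindfulness approaches seek to strengthen abilities to become aware of, tolerate, and adaptively self-regulate uncomfortable sensations", with food cravings as the example. Section 5.2 lists the content added for Ed+MBI, including "paying attention, noticing habit loops, understanding brain science and food/sugar addiction, disrupting emotional and stress eating". The behavioural content that section 5.2 gives to everyone is goal-setting and self-monitoring of weight, diet and activity; no craving training is named there. Section 3 says that neither participants nor staff are blinded.

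Section 9.6 makes the between-group comparison of change from baseline the primary analysis. It relates the mechanism measures to ketones and to carbohydrate intake from 24-hour recall by linear regression.

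**The concern.** The outcome passes through a filter: the participant must notice a craving and attribute the eating to it. One arm is trained on that filter and the other is not. The same episode could therefore be classified differently in the two arms after training, with no difference in what was eaten. Section 6.2.2 itself describes the target behaviour as often short and automatic, which is the kind of episode an untrained person may not label.

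Randomisation and change from baseline do not remove this, because the shift would arise after baseline in one arm. The advantage claimed for EMA in section 2.2 is less retrospective reporting bias, which is a different problem.

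At stake is how R61 Aim 2 is read. A positive EMA contrast could partly reflect reluctance to label, and a null one could partly reflect better noticing. The regression of adherence on the EMA measure inherits the same uncertainty.

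**Working it through.** **1. The plan's own figure.** Section 9.2 gives a 10-point difference (30% v 20%), SD 11, 30 per arm, two-sided alpha 0.05 and 80% power. The standard error is 11 × √(2/30) = 2.84, so the noncentrality is 10/2.84 = 3.52, and noncentral-t power on 58 df is 93%. The stated 80% is reproduced with an SD of about 13.6. That mismatch is a separate matter. It is carried here only by showing power under both SDs.

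**2. Which rates are these?** Section 9.2 states the 50% baseline as an EMA measurement and says that it will fall to 30% and 20%. The two follow-up rates are therefore taken as EMA-measured.

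**3. Model.** Measured rate = underlying rate × s, where s is the share of episodes that the participant labels as a response to a craving. The documents give no value of s. **Assumption:** s = 0.80 in untrained people. The underlying rates are then 30/0.80 = 37.5% (Ed) and 20/0.80 = 25% (Ed+MBI). With equal labelling the measured difference is 37.5 × 0.80 − 25 × 0.80 = 10 points.

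**4. Labelling rises in Ed+MBI only (a benefit is hidden).** Ed stays at 30%.

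| s in Ed+MBI | Ed+MBI measured | Difference | Two-sided power, SD 11 | SD 13.6 |
|---|---|---|---|---|
| 0.80 | 20% | 10 | 93% | 80% |
| 0.90 | 25 × 0.90 = 22.5% | 7.5 | 74% | 56% |
| 0.95 | 25 × 0.95 = 23.75% | 6.25 | 58% | 42% |
| 1.00 | 25% | 5 | 41% | 29% |

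Starting from 0.80, the difference can at most be halved. If untrained people labelled only two-thirds of episodes, full labelling in Ed+MBI would give 20/(2/3) = 30%, and the whole difference would vanish.

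**5. Labelling falls in Ed+MBI only (a benefit is mimicked).** Suppose there is no true difference, with 37.5% underlying in both arms.

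| s in Ed+MBI | Ed+MBI measured | False benefit | Chance of significance, SD 11: two-sided / one-sided |
|---|---|---|---|
| 0.72 | 27% | 3 points | 18% / 27% |
| 0.64 | 24% | 6 points | 55% / 67% |

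The one-sided figure is shown because section 9.2 favours a one-sided test for this phase. Only the ratio of the two labelling shares matters here (0.9 and 0.8).

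**6. Is there a check in the plan?** Ketones (section 6.2.4) and unannounced 24-hour recall (section 6.2.2) need no craving label. Section 9.6 uses them as adherence measures and correlates them with the EMA measure. It does not set their between-arm differences against the EMA contrast, and it does not say what to conclude if they disagree.

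**The case against.** The other side has real points.

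- **Off-diet eating is recorded elsewhere.** A reader might infer that eating not labelled as a craving response escapes the trial altogether. It does not: ketones are measured two or three times a week and checked against the meter's memory, and the recalls come without notice. The gap is in the primary contrast, not in the whole data set.
- **The survey is only summarised.** Exact wording and branching are not given, and section 9.1 says EMA will also assess eating in response to emotions. That still requires attribution to a feeling, so it supplies no label-free count.
- **The sample already recognises cravings.** Section 4.1 requires frequent cravings and regular eating in response, and section 6.2.1 confirms this by EMA. Both arms answer the same prompts. This makes a large arm-specific gap less plausible but does not exclude one.
- **Direction.** A reader might infer a bias towards Ed+MBI. The training text directly supports only better noticing, which works against Ed+MBI. Reluctance to label is possible in an unblinded, self-rated arm, but no text describes it.
- **Consequences.** A reader might infer that R61 would be stopped or advanced on this contrast alone. No such rule appears, and Aim 2 also looks at whether the mechanisms predict adherence.
- **Size.** Treating 30% and 20% as true rates before labelling loss would shrink the differences further. The wording of section 9.2 does not support that reading.
- **Construct.** Any sweet or starchy eating is nearer to adherence than to the hypothesised mechanism. That is a reason to keep the craving measure primary, not to omit a companion measure.

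**Conclusion.** The concern holds as a limit on interpretation. As described, the primary outcome depends on craving attribution, one arm is trained in craving awareness, and no planned analysis separates relabelling from a real change in eating. Both positive and null EMA results are open to this doubt.

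The documents do not establish that a labelling shift will occur, which way it would go, or how large it would be. The loss from 10 points to between 7.5 and 5, with power of 74% to 41% at SD 11, rests wholly on the assumed labelling shares. It shows sensitivity and is not an estimate of bias. The logical point does not depend on which SD is right. The remedy is a cheap improvement that leaves the primary outcome and sample size unchanged.

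**What to change.** **Section 6.2.2.** Add one yes/no item, asked first at every EMA prompt in both arms and from the baseline burst onward: has the participant eaten any sweet or starchy food since the last prompt, whether or not there was a craving? State the look-back for the first prompt of a burst.

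**Section 9.6.** Keep craving-related eating as primary. Beside it, report by arm with confidence intervals:

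- the unconditional item;
- craving occurrence;
- eating given a craving;
- the planned ketone and 24-hour recall results.

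State in advance that a difference in the craving-labelled measure without a corresponding difference in the label-free measures will be reported as a possible labelling effect. Do not make the claim depend on a bare same-direction rule: if the unconditional item did not truly differ between arms, its estimate would agree in sign by chance about half the time.

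**Cost.** One short item at 9 prompts per burst (3 a day for 3 days) and a few more summaries, with slightly more participant burden. The new item is still unblinded self-report, so it removes the need for craving attribution but not other reporting bias. At 30 per arm the label-free comparisons may be imprecise, so their intervals should be read and not only their p-values.

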1.2 Secondary Objectives

Secondary mechanistic outcomes: We have four additional mechanistic measures to assess our hypothesis that mindfulness training will enhance dietary adherence:

- Enhanced ability to reduce craving-related eating/decreased impulsivity as measured by the Relative Reinforcing Value of Food or Delayed Discounting task.
- Decreased stress-related eating as measured by the Palatable Eating Motives Scale (PEMS) subscale for stress-related eating as a coping mechanism.
- Decreased emotion related eating as measured by the Emotional Overeating Questionnaire.
- Improved resilience (resumption of dietary adherence) after dietary non-adherence occurs. Our key measure will be the time from a ketone measure of < 0.2 mmol/L to higher levels of > 0.2 mmol/L, indicating a return to nutritional ketosis after a period of consuming foods that depress ketosis.

Secondary clinical outcomes:

- Glycemic control, using HbA1c. We view improving HbA1c as the primary clinical outcome that we seek to improve in subsequent studies.
- Fasting glucose
- Homeostatic model assessment (HOMA) index of insulin resistance (computed from insulin and fasting glucose measures)
- Weight
- Adherence to diet measured by 24-hour diet recall and by ketone measures

In the R33 phase, we will test the hypothesis that the Ed+MBI arm will have better dietary adherence than the Ed arm. We hypothesize also that reducing maladaptive responses to stress will promote dietary adherence.

2. BACKGROUND AND RATIONALE

2.1 Background on Condition, Disease, or Other Primary Study Focus

Type 2 diabetes mellitus (T2DM) is a major public health issue. T2DM is the most costly chronic disease in the United States, with 10% of healthcare dollars spent on T2DM.¹ There are currently about 22 million persons in the United States and about 350 million people worldwide with T2DM.^{1,2} Lifestyle modification is a key component of disease management, but achieving long-term adherence to diet recommendations is a central challenge. Diet and exercise can improve glycemic control in T2DM. Lowering glycosylated hemoglobin (HbA1c), a central measure of glycemic control in T2DM, reduces the risk of complications such as nephropathy and retinopathy.³ The Look AHEAD study, based on the successful Diabetes Prevention Program intervention, is the largest trial of lifestyle interventions in T2DM to date. Participants in the intensive lifestyle intervention arm (relative to the control arm) in this trial lost 8 kg more weight and lowered HbA1c by 0.6% after one year.⁴ However, these advantages diminished to a 1.6 kg weight and 0.05% HbA1c difference at the end of the trial (with a median of 9.6 years of follow-up).⁵ These weaker long-term benefits highlight the importance of developing sustainable approaches to diet intervention in T2DM.

2.2 Study Rationale

Eating in response to food cravings, defined as intense urges or desires to eat specific foods,⁶ emotional eating, and mindless eating pose challenges to adherence to diet recommendations, especially for people with diabetes.^{7,8} Efforts to achieve a healthy food environment, including changes in the foods available in one's home and workplace, are an important step in adherence to a healthy diet for T2DM. However, foods that are inconsistent with a healthy diet in T2DM are everywhere. Of packaged foods sold in the United States, 74% have added sugars.⁹ Seeing desirable food can trigger spontaneous simulations of eating it, including thinking about the pleasure of eating the food, and can

activate brain areas involved in taste and reward as if one were actually eating the food.^{10,11} Thus the abundant food cues sets up people for frequent cravings and easy access to highly sweetened foods. Enhanced behavioral strategies that support long-term dietary adherence in T2DM are critically needed not only for management of diabetes but for pre-diabetes and obesity, each of which affect over one-third of adult Americans.^{12,13}

Mindfulness skills have the potential to enhance dietary adherence. We address an area NCCIH identifies as a high priority for mind-body intervention research in RFA-AT-16-005: “behavior change to promote healthy behaviors such as healthy eating.” Jon Kabat-Zinn developed the Mindfulness-Based Stress Reduction (MBSR) program and describes mindfulness as “paying attention on purpose, in the present moment, and nonjudgmentally, to the unfolding of experience moment to moment.” One hypothesized mechanism by which mindfulness may increase long-term dietary adherence is by equipping individuals with the skills to acknowledge and experience food cravings and negative emotions without acting on them and by increasing resilience after temporary lapses in dietary adherence. Mindfulness approaches seek to strengthen abilities to become aware of, tolerate, and adaptively self-regulate uncomfortable sensations (e.g., food cravings) without maladaptive responding (e.g., craving-related eating).¹⁴ Current neurobehavioral models of eating behavior are based on experimental data showing that obese persons respond to pictures of high-calorie foods with greater activation of brain regions hypothesized to mediate motivational effects of food cues.¹⁵ This suggests that heightened sensitivity to palatable food cues may confer greater vulnerability to overeating. Other experimental data show that greater sensitivity to palatable food cues is associated with increased palatable food intake only in persons with lower inhibitory control.¹⁶ These data suggest that strengthening inhibitory control may enhance dietary adherence, and may be especially useful for individuals who are more susceptible to palatable food cues. Mindful awareness of one’s own experience, a core focus of mindfulness training, can reduce both impulsive responses to attractive food stimuli and the thoughts that they trigger in experimental situations.¹⁷

In our theoretical model, mindfulness training directed at eating behavior strengthens the ability to tolerate negative states (e.g., cravings for foods incompatible with one’s dietary goals) without enacting maladaptive automatic behaviors (e.g., eating in response to craving), providing a potentially powerful tool for facilitating healthy eating behavior. Given the relations above, we focus on cravings as a primary mechanism for overeating. Our intervention choice, mindfulness, may have the unique ability to help people tolerate cravings and reduce compulsive eating, as our pilot data suggests.

Mindfulness training can also bolster adaptive stress management, and thereby holds the potential to reduce stress-eating, which is associated with poorer metabolic health. . People who report stress-eating may be more vulnerable to developing obesity and metabolic syndrome.¹⁸ Mindfulness is associated with lower stress-eating in people with diabetes, cross-sectionally.⁸ Our mindfulness-based intervention will include MBSR-based stress management components and Mindfulness Based Eating Awareness Training,¹⁹ which, taken together, act on stress-eating behavior, as well as eating in response to any negative emotions (emotional eating). Improving stress management skills may also directly influence blood glucose levels in T2DM via improvements in maladaptive neuroendocrine responses, as stress hormone responses counteract insulin thereby increasing blood glucose levels..^{20,21} Strengthening adaptive coping responses to stress may also facilitate health behavior such as adhering to medication, diet, and exercise regimens.^{22,23}

There are important new challenges in optimizing mindfulness-based interventions for diet change. This proposal builds on our group’s study of the effects of including mindfulness-based eating and stress management to achieve weight loss and improve metabolic parameters in persons with obesity, but without T2DM (SHINE). While we found evidence of benefits in weight, lipids, and fasting

glucose, we also found variability in participant outcomes by teacher that highlights the need to further optimize the intervention manual/approach.

Carbohydrate restricted (CR) diets can provide an important biomarker (ketone level) for dietary adherence and may improve glucose control in T2DM. Current recommendations from the ADA suggest that a variety of carbohydrate levels may be appropriate for persons with T2DM, including reduced carbohydrate diets.²⁴ We aim to restrict carbohydrates to approximately 10% of caloric intake, or about 50 g/day in this study for several reasons. This induces a low level of ketone production, which has been termed “nutritional ketosis.” This provides an *important biomarker* for dietary adherence that we aim to utilize in this study (See Measures in the Approach section). Unlike diabetic ketoacidosis, nutritional ketosis is a stable metabolic state associated with potential health benefits in persons with T2DM. Several studies suggest that lowering carbohydrate intake to this range can improve glucose control, insulin resistance, plasma triglycerides, plasma C-reactive protein, and body weight.²⁵⁻³¹ For example, in a short-term study conducted in a metabolic ward, 10 overweight persons with T2DM consumed their usual diets for 7 days, followed by a CR diet (21 g/day carbohydrate) for 2 weeks. Participants’ mean 24-hour plasma profiles of glucose levels normalized, mean HbA1c decreased from 7.3% to 6.8%, and insulin sensitivity improved by approximately 75% on the carbohydrate restricted diet.³² Our group has compared a CR diet (< 50 grams/day carbohydrate) to a conventional calorie-restricted diet for T2DM and found a significantly greater improvement in mean HbA1c in those on the carbohydrate restricted diet group (see Preliminary data in Approach for further details).³¹

As in other diet interventions, adherence remains a key challenge. In our diabetes pilot study, we found that with limited long-term behavioral support, by 12-months the improvements in HbA1c had declined -0.2% (-0.8 to 0.4, p = .5; unpublished data). While we considered including different diets in the current study, our primary focus is on the role of mindfulness-based intervention components on dietary adherence. We thus choose to keep the diet consistent across groups, and believe a low carbohydrate diet is a good choice because it offers an effective biomarker of adherence, potential health benefits for persons with T2DM, and clear adherence challenges.

This study includes several key innovations.

1. Our theoretical mechanistic model is novel and highly specific, but with broad significance. Cravings and stress lead to overeating sweets and carbohydrate, which worsen glucose control in T2DM. Our mindfulness intervention is uniquely tailored to focus on regulation of both cravings and stress. This pathway is important in obesity and related disorders, and addiction, and thus has the potential for widespread impact of tailored mindfulness-based behavioral interventions.
2. We measure eating in response to cravings and stress using innovative ecological momentary assessment (EMA) methods. We have developed a novel EMA tool to measure these behaviors *in vivo* and have over 90% compliance in our pilot studies. EMA methods reduce well-known biases of retrospective reporting in traditional single-administration self-report measures of eating.³³
 - a. We use an innovative biomarker approach to assessing dietary adherence to carbohydrate restriction using blood ketone monitoring. While this measure has been previously used in studies of carbohydrate restricted (CR) diets to monitor adherence to CR (including a study by our group) within a study diet arm, to our knowledge, this study would be the first time ketone monitoring will be used as a biomarker to compare different approaches (i.e., mindfulness versus education only) to achieving dietary adherence.
 - b. We use an adaptive intervention design to test optimization of the maintenance phase intervention. Our goal is long-term adherence to health behavior change.

Few mindfulness-based interventions (MBI) have examined long-term maintenance strategies, despite the potential importance. In optimizing a maintenance phase intervention, we believe that calibrating the intervention dose based on how participants are doing may be important. Adaptive intervention designs assign intervention intensity/dose based on how a participant is doing (note that despite similar names and certain parallels. Adaptive intervention designs are a different entity from adaptive clinical trials: In adaptive interventions, therapy is individualized based on decision rules, whereas in adaptive clinical trials, the overall trial protocol is modified in response to accruing trial data.³⁴ We draw on Sequential Multiple Assignment Randomized Trial (SMART) design methods to test adaptive intervention strategies in the maintenance period.³⁵ To our knowledge, adaptive intervention designs have not been tested before in published research on MBI interventions. Testing such approaches to MBI maintenance provides an innovative approach that is well-suited to our particular intervention and will provide an important model for future MBI research

